#### **Male Subjects**

1. Male subject must be willing to remain sexually abstinent (consistent with lifestyle) or with female partner(s) of childbearing potential must ensure that their partner(s) uses the methods of birth control as outlined for female subjects above.

# 24. APPENDIX V. TOTAL BLOOD VOLUMES

An estimated 37.5 mL of blood will be collected for study assessments from each subject during the study as shown in Table 8.

**Table 8:** Blood Collection Volumes (mL)

Visit	1E	2E	3E	4E	5E	6E	7E	8E	9E	10E /ET	11E	12E	13E /EOS	
Week	Baseline	1	2	4	6	10	14	18	22	26	27	28	29	
Day (±3°)	0	7	14	28	42	70	98	126	154	182	189	196	203 (±7)	
Lab test														Total
Hematology	CO						2			2			2	6
Chemistry	CO						8.5			8.5			8.5	25.5
Thyroid Panel b	CO													
Lipid Panel b	CO													
Sex Hormone Tests	СО						2			2			2	6
Serum pregnancy (Females) a,b	СО													
TOTAL	0	0	0	0	0	0	12.5	0	0	12.5	1 60		12.5	37.5

Abbreviations: CO = Carried over from core study (no additional blood drawn; 0 mL), EOS = End of Study; ET = Early Termination = Visit.

 $a \ge 8$  years of age.

b Included in serum chemistry sample.

<sup>c Unless otherwise specified.

1. GLOSSARY OF ABBREVIATIONS

Abbreviation	Full Form
ADHD	attention deficit hyperactivity disorder
ADHD RS-IV HV	ADHD Rating Scale Version IV - Home Version (modified for investigator administration)
AE	Adverse event
ALT	alanine aminotransferase
AST	aspartate aminotransferase
ATC	Anatomical Therapeutic Chemical Classification
β-hCG	beta-human chorionic gonadotropin
BMI	Body mass index
BUN	Blood urea nitrogen
CGI-S	Clinical Global Impression - Severity
Conners 3-P	Conners 3 rd Edition - Parent
CSR	Clinical study report
CSHQ	Children's Sleep Habits Questionnaire
C-SSRS	Columbia - Suicide Severity Rating Scale
DB baseline	double-blind baseline
DB treatment	double-blind treatment (i.e. treatment received during SEP360-202)
DBL	database lock
DESS	Discontinuation-Emergent Signs and Symptoms (DESS) Scale
DSM-5	Diagnostic and Statistical Manual of Mental Disorders, Fifth Edition
DSM-IV-TR	Diagnostic and Statistical Manual of Mental Disorders, Fourth Edition; Text Revision
ECG	electrocardiogram
eCRF	electronic case report form
EOS	end of study
ET	early termination

Abbreviation	Full Form
HR	heart rate
ICH	International Conference on Harmonization
ITT	intent-to-treat
KM	Kaplan-Meier
LOCF	last observation carried forward
MedDRA	Medical Dictionary for Regulatory Activities
mg	milligram
n/a	not applicable
OL baseline	open-label baseline
PR	time between P wave and QRS in electrocardiograph
PT	preferred term
PWC	Physician Withdrawal Checklist (PWC)
QRS	electrocardiographic wave (complex or interval)
QT	electrocardiographic interval from the beginning of the QRS complex to the end of the T wave
QTc	QT interval corrected for heart rate
SAE	serious adverse experience/event
SAP	Statistical Analysis Plan
SD	standard deviation
SE	standard error
SOC	system organ class
TEAE	treatment-emergent adverse event
WBC	white blood cells
WHO	World Health Organization
WHODRUG	World Health Organization Drug Dictionary
WFIRS-P	Weiss Functional Impairment Rating Scale - Parent Report

2. PURPOSE

The purpose of this statistical analysis plan (SAP) is to ensure that the efficacy and safety analyses defined by appropriate data listings, summary tables, and figures, as well as statistical methodologies, are outlined in this document and provide valid conclusions about the study objectives.

2.1. RESPONSIBILITIES

INC Research will perform the statistical analyses and is responsible for the production and quality control of all tables, figures, and listings.

The analyses of efficacy, safety for the clinical study report (CSR) are planned to be completed after the database lock (DBL).

3. STUDY OBJECTIVES

3.1. PRIMARY OBJECTIVE

To evaluate the long-term safety and tolerability of flexibly-dosed dasotraline in children and adolescents with ADHD by the incidence of adverse events (AEs; or serious AEs [SAEs]), and AEs (or SAEs) leading to discontinuation.

3.2. SECONDARY OBJECTIVE(S)

The secondary objectives are:

- To evaluate the long-term safety and tolerability of flexibly-dosed dasotraline in children and adolescents with ADHD by assessing clinical laboratory evaluations, vital signs, physical examinations, body height and weight, 12-lead electrocardiograms (ECG), Tanner Staging, Children's Sleep Habits Questionnaire (CSHQ), and the frequency and severity of suicidal ideation and suicidal behavior using the Columbia - Suicide Severity Rating Scale (C-SSRS) Children's Assessment.
- To assess the long-term effectiveness of dasotraline in children and adolescents with ADHD using the following assessments:
 - the ADHD Rating Scale Version IV - Home Version (modified for investigator administration) (ADHD-RS-IV HV)

- the Clinical Global Impression - Severity (CGI-S)
- the Conners 3rd Edition Parent (Conners 3-P)
- To evaluate health-related quality of life and functional impairment in children and adolescents with ADHD using the Weiss Functional Impairment Rating Scale - Parent Report (WFIRS-P).
- To assess potential withdrawal symptoms following discontinuation of dasotraline treatment using the following assessments (administered during the withdrawal period):
 - Discontinuation-Emergent Signs and Symptoms (DESS) Scale
 - Physician Withdrawal Checklist (PWC)

4. STUDY DESIGN

4.1. BRIEF DESCRIPTION

This is an open-label, flexibly-dosed, 26-week extension study in children and adolescents with ADHD who have completed 6 weeks of double-blind treatment in the core study (SEP360-202). Subjects who meet all eligibility criteria will transition directly from the core study and will not need to complete the End of Study (EOS) visit in the core study. Subjects will take the first dose of open-label study drug in this extension study on Day 1, the morning following the open-label (OL) Baseline visit. Subjects will continue to take study drug for 26 weeks, at approximately the same time each morning including on the days when clinic visits occur. Dasotraline will be dosed at 2 mg/day for the first week of the study (Days 1 - 7). Subjects will then be flexibly dosed (2, 4, or 6 mg/day) thereafter beginning on Day 8 based on the investigator's assessment of effectiveness and tolerability. After the OL Baseline visit, subjects will return to the clinic weekly for the first 2 weeks, once every 2 weeks for the next 4 weeks, then once every 4 weeks for the remainder of the treatment period for clinical evaluation, and once at the end of the withdrawal period (Visit 13E). At the approximate midpoint between the scheduled monthly visits (i.e., 14 ± 2 days after a visit) during the treatment period, the site staff will contact the subject's parent/legal guardian via telephone, text, or email in order to evaluate the safety of the subjects as well as to remind subject/parent/legal guardian about adherence to study drug administration and upcoming visits, following which, if necessary, an unscheduled visit can be arranged.

All assessments will be performed as per the schedule of assessment in [Appendix 1](#).

4.2. DETERMINATION OF SAMPLE SIZE

This study is projected to enroll up to 330 subjects based on the number of subjects who complete the core study.

5. STUDY ENDPOINTS

5.1. PRIMARY ENDPOINT

The primary endpoint is:

- The incidence of overall AEs (or SAEs), and AEs (or SAEs) leading to discontinuation.

5.2. SECONDARY ENDPOINTS

The secondary endpoints are:

- Clinical laboratory evaluations (serum chemistry, hematology, lipid panel, thyroid function panel, urinalysis, sex hormones).
- Clinical evaluations (vital signs, physical examination, body height and weight, Tanner Staging, and 12-lead ECG).
- Frequency and severity of suicidal ideation and suicidal behavior using the C-SSRS.
- Change in CGI-S score.
- Change in ADHD-RS-IV HV total score.
- Change in the inattentiveness and hyperactivity subscales of the ADHD-RS-IV HV.
- Change in Conners 3-P total score and subscale scores (Oppositional, Cognitive problems, Hyperactivity, and ADHD Index).

- Change in CSHQ total score and 8 subscale scores (bedtime resistance, sleep onset delay, sleep duration, sleep anxiety, night wakings, parasomnias, sleep disordered breathing, and daytime sleepiness).
- Change in WFIRS-P total score and 6 domain scores (family, school learning behavior, life skills, child's self-concept, social activities, and risky activities).
- Symptoms of withdrawal using:
 - PWC score
 - DESS score

6. GENERAL ASPECTS FOR STATISTICAL ANALYSIS

6.1. GENERAL METHODS

- All analyses and summaries will be produced using SAS[®] version 9.3 (or higher) for windows.
- All statistical summaries will be presented based on the treatment received in the double-blind core study (SEP360-202), called DB treatment. Because the treatment received in SEP360-310 is flexible, the treatment groups for summary in SEP360-310 will be labeled as:
 - placebo / dasotraline flexible,
 - dasotraline 2 mg/day / dasotraline flexible,
 - dasotraline 4 mg/day / dasotraline flexible,
 - dasotraline combined / dasotraline flexible, and
 - total.
- The dasotraline combined group will include those subjects who were treated in SEP360-202 with dasotraline 2 mg/day and dasotraline 4 mg/day.
- Summaries will also be presented by visits (Double-Blind Baseline, Open-Label Baseline, Weeks 1, 2, 4, 6, 10, 14, 18, 22, 26, Week 26 or Treatment Period LOCF,

and EOS). See the details for the DESS and PWC for discussion of the display of visits for those summaries.

- Unless otherwise specified, continuous variables will be summarized with descriptive statistics including: n, arithmetic mean, standard deviation (SD), 95% confidence interval for the mean, median, minimum, and maximum values. All categorical/qualitative data will be presented using frequency counts and percentages. Shift tables will be produced for some assessments and will contain counts and percentages of subjects in each cross-classification level of baseline versus post-baseline assessment. Only subjects with a non-missing value for both baseline and post-baseline, at a given visit, will be included in these tables.
- The listings will be provided using the enrolled population (defined in [Section 8.1](#)). For listings related to analyses conducted using the intent-to-treat population, a flag will be shown in the subject column identifying subjects who were excluded from the intent-to-treat population. In general, the subject listings will be sorted by the treatment group, subject number and assessment date (and time, if applicable).
- Data for unscheduled assessments will be included when selecting worst result for shift analyses, and for summary of normal/abnormal values. The summary of observed value and change from DB baseline and change from OL baseline data will be performed by nominal visits (scheduled visits). Unscheduled assessments will be included in Week 26 or Treatment Period LOCF, as long as that unscheduled assessment was not completed more than 3 days after the last dose of study medication.

6.2. KEY DEFINITIONS

6.2.1. Baseline Value

Two different baseline values are defined for this study.

The first baseline value, called the DB baseline, is the baseline value from the double-blind core study, SEP360-202. This value is the last non-missing assessment value up to and including the day of first dose of study drug in SEP360-202.

The second baseline value, called the OL baseline, is defined as Week 6 (LOCF) from the core study, SEP360-202, which is also the assessment at the start of SEP-360-310. For

the questionnaire based endpoints, domain scores for the Week 6 (LOCF) may come from different assessment dates. This occurs when an incomplete questionnaire was completed at the Week 6 assessment of SEP360-202.

For assessments completed at the EOS assessment, a third baseline value is defined as the last assessment on treatment. This baseline will be the SEP360-310 LOCF value.

6.2.2. Study Day

Study day is defined as the number of days from the date of first dose in the SEP360-310 study to the event/visit date. It is calculated as follows:

If event date falls on or after the date of first dose then

$$\text{Study Day} = \text{Event or Visit Date} - \text{First Dose Date} + 1$$

If event date falls before the date of first dose then

$$\text{Study Day} = \text{Event or Visit Date} - \text{First Dose Date}$$

Hence, the date of first dose is referred to as Day 1. The previous day is Day -1.

6.2.3. Missing Data and Last Observation Carried Forward (LOCF)

Methods for handling missing item responses on the questionnaire instruments (i.e. ADHD-RS-IV HV, Conners 3-P, and WFIRS-P) are described in different sections later on.

If a subject discontinues the study prematurely, the last available data (excluding early termination visit assessments if done more than 3 days after the last dose of study medication, unscheduled assessments after the early termination assessment if done more than 3 days after the last dose of study medication, and Withdrawal Period assessments) will be carried forward to the study endpoint (i.e. the LOCF approach) at Week 26. Visits earlier than the early termination date for subjects who discontinued the study prematurely will be included in the LOCF process, even if they are more than 3 days after the last dose of study medication.

The AE and concomitant medication start/end dates will be imputed based on the rules described in [Appendix 3](#).

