# 6.2. Secondary Endpoints

The secondary endpoints are:

- Clinical laboratory evaluations (serum chemistry, hematology, lipid panel, thyroid function panel, urinalysis, sex hormones).
- Clinical evaluations (vital signs, physical examination, body height and weight, Tanner Staging, and 12-lead ECG).
- Frequency and severity of suicidal ideation and suicidal behavior using the C-SSRS.
- Change in CGI-S score.
- Change in ADHD-RS-IV HV total score.
- Change in the inattentiveness and hyperactivity subscales of the ADHD-RS-IV HV.
- Change in Conners 3-P total score and subscale scores (Oppositional, Cognitive problems, Hyperactivity, and ADHD Index).
- Change in CSHQ total score and 8 subscale scores (bedtime resistance, sleep onset delay, sleep duration, sleep anxiety, night wakings, parasomnias, sleep disordered breathing, and daytime sleepiness).
- Change in WFIRS-P total score and 6 domain scores (family, school learning behavior, life skills, child's self-concept, social activities, and risky activities).
- Symptoms of withdrawal using:
  - PWC score
  - DESS score

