10. DEMOGRAPHICS AND OTHER BASELINE CHARACTERISTICS

10.1. DEMOGRAPHICS AND OTHER BASELINE CHARACTERISTICS

Demographics (collected at enrollment into the SEP360-202 study) (sex, race, ethnicity, age [years], age group [6-9 and 10-12 years], weight [kg], height [cm], body mass index [BMI, kg/m²], and World Health Organization (WHO) z-scores and percentiles for height and BMI) will be summarized by DB treatment and overall for the safety and ITT populations. These values will be referred to as DB baseline values.

The age, age group [6-9 and 10-13 years], weight, height, BMI, and WHO percentiles for height and BMI at the time of enrollment into the SEP360-310 study will be summarized by DB treatment and overall for the safety and ITT populations. These values will be referred to as OL baseline values. Note that some subjects who were 12 years old at entry into SEP360-202 had turned 13 years old at the time of entry into SEP360-310.

Sex, race, age group, and ethnicity will be summarized by using summary statistics for categorical variables (frequencies and percentages). Percentages for sex, race, age group, and ethnicity will be based on the number of subjects within a DB treatment group. The DB baseline and OL baseline values for Age, height, height percentile, weight, BMI, and BMI percentile will be summarized by using summary statistics for continuous variables (number of subjects, arithmetic mean, standard deviation, 95% confidence interval for mean, median, minimum and maximum values).

Age will be calculated as the number of years between date of birth and date of enrollment into the SEP360-202 and SEP360-310 studies.

$$\text{BMI (kg/m}^2\text{)} = \text{Weight(kg)} / (\text{Height(m)})^2$$

Normal age and sex-based percentiles for weight, height, and BMI will be determined using the WHO growth charts.

BMI category: Underweight (< 5 percentile), Normal (≥ 5 - < 85 percentile), Overweight (≥ 85 - < 95 percentile), Obese (≥ 95 percentile).

A listing of demographic data will be provided for the enrolled population.

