12.8. VITAL SIGNS

Vital signs (blood pressure, pulse rate, height, height WHO z-score, weight, BMI, BMI z-score, respiratory rate, and oral temperature) will be monitored at every clinic visit. Respiratory rate and oral temperature will be measured following 5 minutes of supine rest.

At any clinic assessment, orthostatic hypotension (determined by blood pressure measurements only) is defined as having either a ≥ 20 mmHg reduction from supine to standing position in systolic blood pressure (SBP) or ≥ 10 mmHg reduction from supine to standing position in diastolic blood pressure (DBP) or both. Orthostatic tachycardia is defined as heart rate increase ≥ 20 bpm from supine to standing position.

Observed values, change from DB baseline, percent change from DB baseline, change from OL baseline, percent change from OL baseline for each vital sign parameter. will be summarized at each visit by DB treatment and overall.

In addition, the markedly abnormal post-baseline vital signs results will also be summarized for subjects with at least one markedly abnormal value during the treatment period. A listing will be provided for all markedly abnormal vital signs. A shift table will be presented comparing shifts from the baseline visit to Week 26 LOCF. Percentages will be based on the number of safety subjects with a non-missing value for both the baseline and post-baseline visit for the given vital sign. A shift table for BMI classification will also be presented comparing shifts from the baseline visit to Week 26 LOCF.

Parameter (unit)	Age (years old)	Markedly Low	Markedly High
SBP (supine, standing) (mmHg)	6-12	Value ≤ 70 and ≥ 20 decrease from baseline	Value ≥ 120 and ≥ 20 increase from baseline
	13-18	Value ≤ 90 and ≥ 20 decrease from baseline	Value ≥ 135 and ≥ 20 increase from baseline
DBP (supine, standing) (mmHg)	6-12	Value ≤ 40 and ≥ 15 decrease from baseline	Value ≥ 80 and ≥ 15 increase from baseline
	13-18	Value ≤ 50 and ≥ 15 decrease from baseline	Value ≥ 90 and ≥ 15 increase from baseline
Pulse rate (supine, standing) (bpm)	6-10	Value ≤ 60 and ≥ 15 decrease from baseline	Value ≥ 135 and ≥ 15 increase from baseline
	11-18	Value ≤ 50 and ≥ 15 decrease from baseline	Value ≥ 120 and ≥ 15 increase from baseline
SBP orthostatic criteria (mmHg)	~	≥ 20 decrease from supine to standing position	NA
DBP orthostatic criteria (mmHg)	~	≥ 10 decrease from supine to standing position	NA

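### The general LOCF rule reaches raw height and weight, so with normal growth and any dropout the LOCF row understates 26-week height gain, and weight gain if the underlying trend is upward

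*SAP*

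**What the plan says.** SAP 6.2.3 sets one rule for early stoppers: the last available value "will be carried forward to the study endpoint (i.e. the LOCF approach) at Week 26". It leaves out early-termination assessments made more than 3 days after the last dose, and Withdrawal Period assessments. It exempts no variable.

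SAP 6.1 lists the rows of the by-visit summaries as DB baseline, OL baseline, then "Weeks 1, 2, 4, 6, 10, 14, 18, 22, 26, Week 26 or Treatment Period LOCF", and EOS. An observed Week 26 row and an LOCF row therefore stand next to each other.

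SAP 12.8 includes among the vital signs "height, height WHO z-score, weight, BMI, BMI z-score, respiratory rate, and oral temperature". For each parameter it asks for "Observed values, change from DB baseline, percent change from DB baseline, change from OL baseline" and percent change from OL baseline, at each visit. Within 12.8, LOCF is named only for shift tables: "A shift table will be presented comparing shifts from the baseline visit to Week 26 LOCF", and likewise for BMI classification.

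The 12.8 list has no weight z-score. SAP 10.1 says that age- and sex-based percentiles for weight, height and BMI will be derived from the WHO charts, but no by-visit summary of weight percentile is planned. No section says at what age a z-score is computed. SAP 10.1 gives ages 6–13 at OL baseline. Protocol 6.2 makes body height and weight secondary endpoints.

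**The concern.** Carrying a value forward assumes that it would not have changed. For a child's height that is wrong by construction: a Week 4 height placed in the Week 26 LOCF row leaves out 22 weeks of growth. The row then mixes growth with attrition, and its mean falls as dropout rises or comes earlier, whatever the drug does.

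This falls on safety endpoints of known interest. Protocol 4.3 reports decreased appetite in adults, and decreases in mean weight that were generally larger at the higher dose. SAP 6.1 attaches a 95% confidence interval to each mean, so the row would look precise around a value that is not the 26-week gain. Columns are by DB treatment, so different dropout timing alone would give the columns different raw LOCF gains. Weight is the most exposed because no age-adjusted by-visit summary stands beside it.

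**Working it through.** The plan states no growth, dropout or power figure, so there is nothing to reproduce. The 330 subjects are a projection.

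**Inputs from the documents:** 26 weeks of treatment; 6 weeks of core study before OL baseline; up to 330 subjects; dropouts not replaced (Protocol 13.1).

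**Assumptions, not in the documents:** dropout share *d* of 10–40%; mean dropout week *w* of 13 (evenly spread) or 7–10 (early); linear growth; no drug effect; dropout unrelated to growth.

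**Formula from OL baseline.** Let *G* be the true 26-week gain. Completers contribute *G*; a child last measured at week *w* contributes *G* × *w*/26. So

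expected LOCF gain = *G* × [(1 − *d*) + *d* × *w*/26]

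relative shortfall = *d* × (1 − *w*/26)

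The growth rate cancels out of the relative shortfall.

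| *d* | *w* | Calculation | Shortfall |
|---|---|---|---|
| 10% | 13 | 0.10 × 0.500 | 5% |
| 20% | 13 | 0.20 × 0.500 | 10% |
| 30% | 13 | 0.30 × 0.500 | 15% |
| 40% | 13 | 0.40 × 0.500 | 20% |
| 20% | 10 | 0.20 × 16/26 | 12.3% |
| 30% | 8 | 0.30 × 18/26 | 20.8% |
| 40% | 8 | 0.40 × 18/26 | 27.7% |
| 40% | 7 | 0.40 × 19/26 | 29.2% |

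**From DB baseline** the full span is 32 weeks, so the shortfall is *d* × (26 − *w*)/32. The three cases with *w* of 10, 8 and 8 become 0.20 × 16/32 = 10%, 0.30 × 18/32 = 17% and 0.40 × 18/32 = 23%.

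**In centimetres**, at an assumed 5.5 cm/year: *G* = 5.5 × 182/365.25 = 2.74 cm. With even dropout of 20%, 30% and 40% the LOCF row shows 2.47, 2.33 and 2.19 cm, which is 0.27, 0.41 and 0.55 cm short.

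**In kilograms**, at an assumed 3 kg/year: *G* = 1.49 kg. The same dropout gives 1.35, 1.27 and 1.20 kg.

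**Against the confidence interval.** A simulation (330 children, 2,000 runs, same growth rates, even dropout) gave a half-width of about 0.10 cm for height. The interval lay below the true gain in essentially all runs at 20–40% dropout. For weight the half-width was about 0.13 kg, and the interval lay below the true gain in about 57%, 90% and 99% of runs at 20%, 30% and 40%. These half-widths imply assumed SDs of change of about 0.10 × √330/1.96 = 0.93 cm and 0.13 × √330/1.96 = 1.20 kg. Columns for single DB groups are smaller and their intervals wider.

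**Z-scores.** With no drug effect, a height z-score computed at the age on the measurement date has mean LOCF change of zero at 20%, 30% and 40% dropout. If a carried-forward height is instead scored at the nominal Week 26 age, the artefact returns. With an assumed height SD of 6 cm it is about −0.27/6 = −0.05 at 20% dropout and −0.55/6 = −0.09 at 40%.

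**The case against.** The strongest reply is that the plan already holds the remedy. The row is named "Week 26 or Treatment Period LOCF", which a careful reader takes as the last on-treatment value, and an observed Week 26 row precedes it. Height and BMI z-scores are summarised at every visit, and anyone asking about growth would turn to them. SAP 12.8 itself names LOCF only for shift tables, so the raw LOCF row comes from the general rule in 6.1. The documents give no dropout rate; at 10% even dropout the shortfall is only 5%.

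Most of this stands and limits the harm. Three things remain. The row is still planned, with a mean and an interval. The z-scores protect only if they use age on the measurement date, which the SAP does not state. Weight has no by-visit z-score at all.

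A reader might go further and infer that the table would show slowed growth or growth suppression, or that column differences would look like a drug effect. The documents do not support that. Raw rows carry no growth norm and would show a smaller positive gain. All columns receive flexible dasotraline, and Protocol 15 plans no inference for treatment comparison.

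Simply deleting every raw LOCF row would also be wrong. Children who stop early, possibly because of weight loss, would drop out of the endpoint summary of weight, with no weight z-score to replace it.

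**Conclusion.** The point holds as a fault in one set of descriptive rows. For height the direction is certain given positive growth and any dropout before Week 26: the raw LOCF mean understates the 26-week gain. The size from OL baseline is about 5–20% for assumed even dropout of 10–40%, and about 12–29% for assumed early dropout of 20–40%. It is less from DB baseline. These figures rest on linear growth and on dropout rates and timing that the documents do not give.

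For weight the same arithmetic applies only if the underlying trend is gain. If the drug causes loss, carrying forward could exaggerate it (loss followed by regain) or mask it (continuing loss). No figure is offered for raw BMI, which need not rise in a straight line.

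The observed rows and the height and BMI z-scores mean that growth can still be read correctly from the planned output. The gaps to close are the missing by-visit weight score and the unstated age for z-scores.

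**What to change.** In SAP 12.8:

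1. Report raw height at observed visits only, and leave it out of the Week 26 LOCF row.
2. Add a by-visit weight z-score, or summarise by visit the weight percentile from the reference already named in SAP 10.1. Confirm first that the reference gives weight values across the whole 6–13 age range.
3. State that all z-scores, including those carried forward, use age on the measurement date. Base growth conclusions at the LOCF endpoint on the z-scores.
4. Keep the raw weight LOCF row so that early stoppers' weight data are not lost. Label it as last on-treatment value, not as 26-week growth.
5. Optionally add height velocity (cm/year) for subjects with at least 12 weeks between measurements, since shorter intervals are noisy. Note that it excludes earlier dropouts.

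The cost is SAP wording, a few derived variables and one row fewer. No new data are collected.

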#### 17.3. Informed Consent

The informed consent and assent forms will be approved by the Sponsor/CRO prior to submission to the IRB/IEC. The Sponsor/CRO may provide a template informed consent/assent form to be qualified by each research facility to conform to local requirements. All informed consent/assent forms must contain the minimum elements as mandated by ICH GCP, applicable local law(s) and regulations and will be subject to Sponsor/CRO approval as well as IRB/IEC approval. The Sponsor/CRO may submit informed consent/assent forms to a central IRB/IEC for review and approval or favorable opinion contingent upon the Investigator's permission and review

Before recruitment and enrollment, each prospective subject and at least one parent/legal guardian will be given a full explanation of the study, allowed to read the approved informed consent/assent forms and be provided ample time and the opportunity to ask any questions that may arise. Once all questions have been answered and the Investigator is assured that the prospective subject/parent/legal guardian understands the implications of participating in the study, the prospective subject and at least one parent/legal guardian will be asked to give consent/assent, as appropriate, to participate in the study by signing the informed consent/assent form unless otherwise instructed by the IRB. As part of the consent/assent process, each prospective subject/parent/legal guardian must consent/assent to direct access to his/her medical records for study-related monitoring, auditing, IRB/IEC review, and regulatory inspection. It should be clearly explained to each prospective subject/parent/legal guardian that participation in each and every clinical visit and assessment is expected. The subject may be discontinued from study medication, but that does not necessarily negate the expectation that the subject will continue to participate in the study through the final visit/assessment. The Investigator will provide a copy of the signed informed consent/assent form to each subject/parent/legal guardian, and will record the date of the informed consent on the CRF.

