6.2.4. Visit Windows

All data will be organized and analyzed according to the scheduled times as outlined in the protocol and by the visit denoted on the electronic case report form (eCRF) except for early termination (ET) visits during the treatment period.

If a subject terminates early and within the 26-week treatment period, the ET visit will be remapped based on the study day of the visit as follows.

ET Day Criteria	Visit
$1 \leq \text{study day} \leq 10$	Week 1
$11 \leq \text{study day} \leq 17$	Week 2
$18 \leq \text{study day} \leq 31$	Week 4
$32 \leq \text{study day} \leq 45$	Week 6
$46 \leq \text{study day} \leq 73$	Week 10
$74 \leq \text{study day} \leq 101$	Week 14
$102 \leq \text{study day} \leq 129$	Week 18
$130 \leq \text{study day} \leq 157$	Week 22
$158 \leq \text{study day}$, but not more than 3 days after treatment termination	Week 26

If a subject already has a scheduled visit at the mapped visit time, then the ET visit will be assigned as unscheduled at that mapped study week. If more than 1 observation is collected at a scheduled visit after baseline, the earliest value (based on collection or visit date) will be used at the visit, and other value(s) will be set as unscheduled. If the early termination visit date is more than 3 days after the date of last dose, then the visit will be assigned as unscheduled if EOS is available, or the visit will be assigned as EOS if EOS is missing.

These ET visit remapping rules will apply to all data points. All tables and figures will be presented by the remapped visit. All data listings will be reported using the visit as denoted on the eCRF.

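### When the early termination visit is late, the SAP can carry forward a value taken off drug and label it the last on-treatment assessment

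*SAP*

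**What the plan says.** For subjects who discontinue prematurely, SAP 6.2.3 carries the last available data forward to Week 26, with three exclusions:

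- ET values ("excluding early termination visit assessments if done more than 3 days after the last dose of study medication");
- some unscheduled values ("unscheduled assessments after the early termination assessment if done more than 3 days after the last dose of study medication");
- all Withdrawal Period assessments.

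It then adds a rule in the other direction. For these same subjects, visits made before the ET date "will be included in the LOCF process, even if they are more than 3 days after the last dose of study medication".

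Three other SAP sections bear on this.

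- SAP 6.2.1, for assessments made at EOS: "a third baseline value is defined as the last assessment on treatment. This baseline will be the SEP360-310 LOCF value".
- SAP 6.1 admits an unscheduled value to the Week 26 or Treatment Period LOCF only "as long as that unscheduled assessment was not completed more than 3 days after the last dose of study medication". It does not distinguish before from after ET.
- SAP 6.2.4 takes an ET visit made more than 3 days after last dose out of the treatment-period visits: "then the visit will be assigned as unscheduled if EOS is available", and otherwise it becomes the EOS visit.

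SAP 12.1 uses the same 3-day limit to separate on-treatment from post-treatment adverse events.

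**The concern.** Elsewhere the SAP draws the line between on and off treatment at 3 days after last dose. In 6.2.3 a visit before the ET date is exempt from that line. Whether an off-drug value counts therefore depends on the kind of visit at which it was taken, not on how long the subject had been off drug.

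Two things are at stake. First, the Week 26 LOCF column, which feeds the effectiveness summaries and the laboratory, vital-sign and BMI shift tables, can mix on-drug and off-drug values. Second, the third baseline can be an off-drug value under an on-treatment name, so that an EOS change meant to show what happens after stopping compares one off-drug value with another. Separately, 6.1 and 6.2.3 give a programmer two different instructions for the same unscheduled visit.

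**Working it through.** There is no sample-size or power figure to reproduce: the 330 is a projection from core-study completers, and no inference is planned. The check is a trace of the rules, followed by an assumption-based range.

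**Rule trace.** Take a hypothetical premature discontinuer with last dose on Day 71 and ET on Day 110. Days off drug = assessment day − 71.

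| Assessment | Day | Days off drug | SAP 6.2.3 | SAP 6.1 |
|---|---|---|---|---|
| Scheduled, Week 10 | 70 | −1 (on drug) | kept | no limit stated |
| Unscheduled | 85 | 14 | not excluded (before ET) | excluded |
| Scheduled, Week 14 | 98 | 27 | kept | no limit stated |
| ET | 110 | 39 | excluded | excluded if 6.2.4 makes it unscheduled |
| Withdrawal Period | 117 | 46 | excluded | not needed |

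The Day 98 value, 27 days off drug, is carried to Week 26 and becomes the third baseline. The Day 110 value is rejected for being off drug. With one 3-day limit for all types, the Day 70 value would be carried.

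**Conflict between 6.1 and 6.2.3.** Remove the Day 98 visit from the example. Under 6.2.3 the last admissible value is Day 85; under 6.1 it is Day 70.

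**How far off drug a kept visit can be.** From Week 6 the visits are 28 days apart, each ±3 days. If the last dose falls on the day of a visit, the next scheduled visit is 28 days later, or at most 28 + 3 + 3 = 34 days. The protocol places EOS 3 weeks ±7 days after the final dose, that is 14 to 28 days. A baseline called on treatment can thus be as far from the last dose as EOS is planned to be. The ET date is the only bound.

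**Which measures are touched** (Schedule of Assessments):

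- *Third baseline:* measures taken at treatment visits before ET and again at EOS. These are vital signs, weight, ECG and C-SSRS, and laboratory tests through Week 14, their only scheduled collection between OL baseline and Week 26/ET.
- *Week 26 LOCF only:* ADHD-RS-IV HV, CGI-S, Conners 3-P, CSHQ and WFIRS-P, none of which is collected at EOS.
- *Not touched:* PWC and DESS, first collected at Week 26/ET.

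**Size, on assumed inputs.** Shift in the LOCF mean = share affected × off-drug shift per affected subject. The documents give neither factor.

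- Low: 1% of 330 = 3.3 subjects; 0.01 × 5 = 0.05 points.
- Middle: 5% of 330 = 16.5 subjects; 0.05 × 10 = 0.5 points.
- High: 10% of 330 = 33 subjects; 0.10 × 15 = 1.5 points.

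The ADHD-RS-IV HV total runs from 0 to 54.

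**The case against.** The strongest defence is that the case should seldom arise. Protocol 13.1 asks subjects who stop study drug to have the ET visit within 3 days of stopping, then the withdrawal calls and EOS. On that path no treatment visit falls more than 3 days off drug before ET. This stands as a limit on frequency. It does not remove the problem: the SAP sentence is written for exactly these cases, and Protocol 17.3 foresees them ("The subject may be discontinued from study medication, but that does not necessarily negate the expectation that the subject will continue to participate"). Protocol 7.1 also counts the 3 days from discontinuation from the study rather than from the drug, so a subject who stops drug, keeps attending and leaves later could satisfy 7.1 and still have a late ET visit.

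A second defence is that keeping these visits is a prespecified choice, in the spirit of a treatment-policy endpoint. That fails on the SAP's own rule, since a treatment-policy endpoint would also keep the late ET value. Nor would it justify the on-treatment label in 6.2.1.

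Third, the laboratory, ECG and vital-sign sections define change from the DB and OL baselines, and none names the third baseline. This is fair. The ECG section does plan a shift from baseline to EOS without saying which baseline. So the third baseline is defined, but its use is not tied to a stated table.

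Fourth, an observed Week 26 row stands beside the LOCF row for the effectiveness scores, and nothing is tested. Both are true and both limit the harm.

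**Conclusion.** The inconsistency is real and worth correcting before database lock, but it is narrow. It needs a premature discontinuer, a late ET visit, and an assessment between 3 days after last dose and the ET date. For such a subject the LOCF value may be off drug, and 6.2.1 then misnames it. The conflict between 6.1 and 6.2.3 on unscheduled visits follows from the text alone.

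The effect on overall summaries is probably small. The range of 0.05 to 1.5 points rests wholly on assumed shares and shifts.

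A reader might infer more, and the documents do not support it:

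- *That off-drug values enter without limit.* The ET date bounds them, and Withdrawal Period values are out.
- *That the affected values are washed out and pull benefit and harm toward none.* No elimination half-life is given, and Protocol 4.3 reports raised heart rate in adults during both treatment and follow-up. The direction is unknown.
- *That EOS changes in effectiveness, or the withdrawal scales, are compromised.* The measure list above rules this out.
- *That the primary endpoint is affected.* Adverse events have their own on-treatment and post-treatment split.

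**What to change.** Replace the last sentence of the LOCF paragraph in SAP 6.2.3. Deleting it is not enough, because the preceding sentence would still admit these visits as the last available data. A rule consistent with 6.1 would be:

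> Only assessments made no more than 3 days after the last dose, whether scheduled, unscheduled or ET, are eligible for Week 26/Treatment Period LOCF and for the third baseline. Scheduled visits made later than this remain in the by-visit observed summaries and the listings, and are flagged.

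Keep the exclusion of Withdrawal Period assessments, refer to this rule from 6.1 and 6.2.1, and state which EOS outputs use the third baseline.

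The cost is a short SAP edit and a matching change in programming, using dates already collected. For a few subjects an earlier value will be carried forward. For measures taken rarely there may be none: in the example, the only scheduled laboratory draw between OL baseline and ET is the off-drug one at Day 98, so that subject would drop out of the laboratory shift table. The SAP should say so and report the number.
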